12.5.2.2 Nicotine and Cotinine Concentrations

The descriptive analysis will be the same as described in Section 12.5.1.1 “COHb in blood and urinary concentrations adjusted for creatinine of MHBMA, 3-HPMA and S-PMA in 24 hour collection”.

The change from the Day -1 sample will be calculated for the Day 5 sample. The concentrations of nicotine and cotinine will be listed and summarized along with this change. Line graphs of the nicotine and cotinine concentration profiles across all study days showing mean and 95% CI will also be produced.

For nicotine and plasma concentrations the change from baseline (Day -1 sample at 08:00 PM - 09:30 PM) on the Day 5 sample will be analyzed using an ANCOVA model with terms for baseline (Day -1) concentration, sex, average daily CC consumption over the last 6 weeks as reported during screening and product. The hypothesis to be tested for each of the biomarkers of exposure of the secondary objectives will be the same as described in Section 12.5.1.2 “Confirmatory Analysis”.

Nicotine and cotinine will also be analyzed in a repeated measures ANCOVA model, as described in section “**12.5.2.1.2 Urinary Biomarkers of Exposure**”.

The data will be presented in the below outputs, the TFL number refers to the TFL number in the accompanying TFL shell document:

TFL number	Title
TABLES	
15.2.4.16	Descriptive Statistics of Plasma Cotinine and Nicotine Concentrations (ng/mL) – FAS
15.2.4.17	Analysis of Change from Day -1 Plasma Cotinine and Nicotine Concentrations on Day 5 – FAS
15.2.4.18	Analysis of Plasma Cotinine and Nicotine Concentrations over the exposure period – FAS
FIGURES	
15.1.2.29	Plasma Cotinine and Nicotine Concentrations (ng/mL) Mean and 95% CI – FAS
LISTINGS	
15.3.3.3	Listing of Plasma Cotinine and Nicotine Concentrations and Sampling Times

12.5.2.3 CYP1A2 Activity

CYP1A2 activity will be measured in plasma on Day -1 and Day 5. In this study the CYP1A2 activity will be calculated using the molar ratio of PX and CAF, as described in Section 7.1.3 “**CYP1A2**”. Descriptive statistics of the values and percent change on Day 5 from Day -1 and supportive listings will be provided.

The analysis will compare the Day 5 values between the CHTP and CC arms. An ANCOVA model will be used with terms for sex, average daily CC consumption over the last 6 weeks as reported during screening and product. The SAS code will be the same as described in Section 12.5.1.1 “**COHb in blood and urinary concentrations adjusted for creatinine of MHBMA, 3-HPMA and S-PMA in 24 hour collection**”.

LS means for each product along with the difference (CHTP - CC) and 95% CI will be presented in the tables.

The data will be presented in the below outputs, the TFL number refers to the TFL number in the accompanying TFL shell document:

TFL number	Title
TABLES	
15.2.4.26	Descriptive Statistics of CYP1A2 Activity (%) – FAS
15.2.4.27	Analysis of CYP1A2 Activity (%) on Day 5 – FAS
LISTINGS	
15.3.4.1	Listing of CYP1A2 Activity and Changes from Baseline

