4. To describe the changes in CYP1A2 enzymatic activity in smokers switching from CC to CHTP 1.0, and in smokers continuing to use CC.

Related Endpoint (Day 5):

Molar metabolic ratio of paraxanthine/caffeine (CAF) in plasma.

5. To describe the daily CHTP 1.0/CC consumption over the Exposure Period in smokers switching from CC to CHTP 1.0 as compared to smokers continuing to use CC.

Related Endpoint (Day 1 to Day 5):

Number of CHTP 1.0 and CC used each day for each subject.

6. To monitor the safety profile during the study:

Related Endpoints:

Incidence of adverse events (AEs)/ serious adverse events (SAEs).

Incidence of CHTP 1.0 malfunctions and misuse, including the incidence of heat source drop off.

Respiratory symptoms: cough assessment by visual analogue scale (VAS). Likert scales, and one open question.

Vital signs.

Spirometry.

Electrocardiogram (ECG).

Clinical chemistry, hematology, and urine analysis safety panel.

Physical examination.

Concomitant medications.

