12.5.1 Primary Analyses

12.5.1.1 COHb in blood and urinary concentrations adjusted for creatinine of MHBMA, 3-HPMA and S-PMA in 24 hour collection

COHb in blood and urinary concentrations adjusted for creatinine of MHBMA, 3-HPMA and S-PMA will be summarized as detailed in Section 12.1.3 “Descriptive Statistics”. In addition, the quantity excreted over 24 hours for each biomarkers of exposure will be presented.

The baseline is as defined in Section 12.1.4 “Definitions for Statistical Data Analysis”,

The values and percent changes from baseline in the concentration adjusted for creatinine will be listed and summarized along with the COHb concentrations and percent changes from baseline. In addition line graphs will be produced for means (and 95% CI) over all timepoints.

The transformed data will be analyzed by means of a generalized linear model using product arm as covariate adjusting for the following stratification parameters: sex and average cigarette consumption over the previous 6 weeks prior to Admission, and log-transformed baseline value of endpoint.

Assumptions of the analysis of variance model will be tested. Markedly non-lognormally distributed BoExp data will be transformed or analyzed by appropriate non-parametric methods.

The SAS code to be used is shown below:

```
Proc mixed data=_data_ ;  
Class product sex cigarette_cons ;  
Model log (Day 5) = log (baseline) sex cigarette_cons product ;  
Lsmean product / pdiff =control('CC') alpha=0.05 cl ;  
Run ;
```

The least squares (LS) means and estimate of the difference along with it's 95% CI will be back-transformed before presenting in the tables. The geometric LS means for each product along with the reduction (i.e: 100% - ratio of CHTP : CC) and 95% CI will be presented in the tables.

In addition line graphs will be produced for product geometric means (and 95% CI) over all timepoints for COHb in blood and urinary concentrations adjusted for creatinine of MHBMA, 3-HPMA and S-PMA.

The data will be presented in the below outputs, the TFL number refers to the TFL number in the accompanying TFL shell document:

TFL number	Title
TABLES	
15.2.3.1	Analysis of Biomarkers of Exposure for the Primary Objectives – FAS
15.2.3.2	Analysis of Urinary Quantity Excreted of MHBMA, 3-HPMA and S-PMA over 24 hours on Day 5 – FAS
15.2.3.3	Descriptive Statistics of Blood COHb (%) – FAS
15.2.3.3.1	Descriptive Statistics of Blood COHb (%) by Sex – FAS

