12.5.3.4 CYP2A6 Activity

CYP2A6 activity will be measured in plasma on Days -1 and 6. In this study the CYP2A6 activity will be calculated using the metabolic ratio of trans 3' hydroxycotinine and cotinine, as described in Section 7.1.4 "CYP2A6". Descriptive statistics of the values and change on Day 6 from Day -1 and supportive listings will be provided.

The analysis will compare the Day 6 values (both absolute and change from baseline) between the CHTP and CC arms. An ANCOVA model will be used with terms for baseline, sex, average daily CC consumption over the last 6 weeks as reported during screening and product. .

The SAS code will be the same as described in Section 12.5.1.1 "COHb in blood and urinary concentrations adjusted for creatinine of MHBMA, 3-HPMA and S-PMA in 24 hour collection"

LS means for each product along with the difference (CHTP - CC) and 95% CI will be presented in the tables

The data will be presented in the below outputs, the TFL number refers to the TFL number in the accompanying TFL shell document:

TFL number	Title
TABLES	
15.2.4.28	Descriptive Statistics of CYP2A6 Activity (%) – FAS
15.2.4.29	Analysis of CYP2A6 Activity – FAS
LISTINGS	
15.3.6.15	Listing of CYP2A6 Activity and Changes from Baseline

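### The CYP1A2 model text in SAP 12.5.2.3 and the SAS code it cites disagree on the baseline term and apparently on the scale; followed as worded, the text gives up precision.

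*SAP*

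**What the plan says.** Secondary objective 4 (SAP 5.2) is "To describe the changes in CYP1A2 enzymatic activity in smokers switching from CC to CHTP 1.0, and in smokers continuing to use CC". Its one endpoint is the paraxanthine/caffeine molar ratio in plasma.

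SAP 12.5.2.3 then makes these statements:

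- Sampling: "CYP1A2 activity will be measured in plasma on Day -1 and Day 5".
- Outcome: "The analysis will compare the Day 5 values between the CHTP and CC arms".
- Model: "An ANCOVA model will be used with terms for sex, average daily CC consumption over the last 6 weeks as reported during screening", with product as the last term.
- Code: identical to that given in 12.5.1.1 for the primary biomarkers.
- Reporting: "LS means for each product along with the difference (CHTP - CC) and 95% CI will be presented in the tables".

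The code in 12.5.1.1 has the model statement "Model log (Day 5) = log (baseline) sex cigarette_cons product". That section goes on to back-transform the LS means and the difference, and to report geometric LS means and a reduction defined as 100% minus the CHTP:CC ratio.

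SAP 12.5.3.4 (CYP2A6, exploratory) is laid out in the same way and cites the same code, but it does list baseline as a term. It adds a second outcome: "The analysis will compare the Day 6 values (both absolute and change from baseline) between the CHTP and CC arms".

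**The concern.** A programmer working from 12.5.2.3 meets two specifications. The text has three terms and no baseline, mentions no logarithm and no back-transformation, and asks for a difference. The code has a log outcome and a log baseline covariate, and its home section turns the result into a ratio. These give different estimates, different CIs and, if the scales differ as they appear to, different effect measures.

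At stake are the estimate and CI in the CYP1A2 analysis table (15.2.4.27). If the text is followed, the between-arm model leaves out a pre-exposure measurement that is scheduled for every subject. If the conflict is not resolved in the SAP, it will be resolved during programming. Under SAP 6.3.2 the statisticians may be unblinded once both SAP finalisation and database lock have passed, so the choice could then be made with the data in view.

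**Working it through.** The documents give no sample size, SD, correlation or power for CYP1A2, so there is no figure of the plan's own to reproduce. The check has two parts.

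**1. Text against code**

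| Item | Text of 12.5.2.3 | Code and reporting of 12.5.1.1 |
|---|---|---|
| Outcome | Day 5 value, no log mentioned | log of Day 5 value |
| Baseline term | none | log baseline |
| Other terms | sex, CC consumption, product | sex, CC consumption, product |
| Effect measure | CHTP minus CC | 100% minus back-transformed ratio |

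The baseline row is a direct contradiction. The scale rows are a probable one. The text never calls the outcome untransformed; that is inferred from the difference, the percent sign in the table titles and the silence on back-transformation. Usage elsewhere in the SAP supports the inference. The puffing topography section (12.5.3.2) cites the same code but names the log transformation of outcome and baseline and reports a reduction from a ratio. The exhaled CO section (12.5.2.1.1) names no log and reports CHTP minus CC. CYP1A2 combines the second style of reporting with the first style of code.

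Nothing else decides the matter. SAP section 9 does not mention CYP1A2. Protocol 12.5.3 plans summaries for secondary endpoints in general, and the model in Protocol 12.4.4 is for biomarkers of exposure.

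**2. Cost of leaving out Day -1**

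Let r be the correlation between Day -1 and Day 5 after allowing for sex and CC consumption, which both versions already include. Ignoring the one residual degree of freedom spent, adding Day -1 multiplies the residual variance by 1 - r² and the CI width by √(1 - r²). The documents give no r; 0.5 to 0.8 is assumed.

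- r = 0.5: variance factor 1 - 0.25 = 0.75; width factor √0.75 = 0.87, so the CI is 13% narrower.
- r = 0.8: variance factor 1 - 0.64 = 0.36; width factor √0.36 = 0.60, so the CI is 40% narrower.
- Outside that range, r = 0.3 gives √0.91 = 0.95.

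There is an offset. SAP 7.1.3 does not calculate the ratio when paraxanthine or caffeine is at LLOQ, so a subject without a Day -1 ratio drops out of the adjusted model. If a fraction m is lost, the width factor is roughly √((1 - r²)/(1 - m)), which stays below 1 while m < r². At r = 0.5 the break-even is m = 0.25, or 20 of the 80 planned subjects.

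**CYP2A6.** In the cited code the day label can be swapped for Day 6. The logarithm cannot be carried over to a change from baseline, because zero and negative changes have none.

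**The case against.** The strongest reply is that this is a drafting slip with an evident intention. The text calls the model an ANCOVA, although both listed adjusters are class variables in the cited code. The code includes baseline, and the parallel CYP2A6 section names it. The code is also plainly a template, since it is cited for endpoints on Days 1, 4 and 6. This makes the intention to adjust for baseline plausible, but the SAP does not say so. It also leaves the scale open: the code points to a log model, while the SAP's habit of pairing a CHTP minus CC difference with no named log points to an untransformed one.

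Several stronger readings are tempting, and the documents do not support them.

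- A reader might infer that a log difference would be printed as percentage points. Section 12.5.1.1 requires back-transformation before tabulation, so a programmer following that section would be led to a ratio.
- A reader might infer that Day -1 is ignored altogether. Section 12.5.2.3 plans descriptive statistics of the percent change from Day -1, and Listing 15.3.4.1 gives changes from baseline. Objective 4 is worded as description in each group, so those summaries address it whichever model is run.
- A reader might infer bias. In a randomised comparison, omitting baseline costs precision only.
- A reader might infer that only a log model is valid. Nothing in the documents shows this for the paraxanthine/caffeine ratio.

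The table shells are in a separate document and may already fix the scale; that cannot be checked here.

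**Conclusion.** The conflict between text and code is real for the baseline term and probable for the scale, and the SAP should resolve it. Followed as worded, the text gives a valid but less precise comparison: adjustment would multiply the CI width by 0.87 to 0.60 if the partial correlation were 0.5 to 0.8. That range is an assumption, and at a low correlation the gain is small. The loss of subjects without a calculable Day -1 ratio is a small downside.

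The reach is narrow: one secondary endpoint with a descriptive objective and no multiplicity adjustment, and the exploratory CYP2A6 analysis alongside it. The primary endpoints, the sample size and the type I error are not touched.

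**What to change.** In SAP 12.5.2.3, add the Day -1 CYP1A2 value to the list of model terms and state one scale, with code and effect measure to match. Either of these would settle it:

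- log Day 5 on log Day -1, sex, CC consumption and product, reported as back-transformed LS means and the CHTP:CC ratio with 95% CI; or
- untransformed Day 5 on untransformed Day -1 and the same other terms, with its own code, keeping the CHTP minus CC difference.

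State also that subjects without a calculable Day -1 ratio are not in the adjusted model, and report how many there are.

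In SAP 12.5.3.4, match code to scale in the same way. If change from baseline is kept as an outcome for CYP2A6, give untransformed code for it.

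The cost is a few lines of SAP text and a check of table shells 15.2.4.27 and 15.2.4.29. No new data are needed.

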12.5.3 Exploratory Analysis

12.5.3.1 Questionnaires

12.5.3.1.1 Urge-to-Smoke Questionnaire of Smoking Urges Brief

The QSU-brief will be administered daily from Days -2 to 5.

All summaries, profiles and analysis will be presented for the CHTP and CC arms.

The change from baseline will be calculated for the total score and the two domain scores (relief and reward). The total score and two domain scores, along with the change from baseline will be summarized. The answers to the individual questions, along with the domain scores, total scores and changes from baseline will be listed.

The profiles of the raw means from baseline to Day 5 for the total score and two domain scores will be produced.

The analysis will compare each post baseline timepoint in the domain and total scores. A repeated measures ANCOVA model will be used with terms for baseline QSU-BRIEF score, sex, average daily CC consumption over the last 6 weeks as reported during screening, product, timepoint, and the interaction between product and timepoint. The interaction term will be removed if $p > 0.1$.

The SAS code to be used is shown below:

```
Proc mixed data=_data_ ;  
Class product sex cigarette_cons time_point ;  
Model reduction = base_QSU sex cigarette_cons product  
product*time_point ;  
Repeated time_point / subject=subject type=un ;  
Lsmean product / diff alpha=0.05 cl ;  
Run ;
```

LS means for each product along with the difference (CHTP - CC) with 95% CI will be presented in the tables.

All figures, summaries and analyses will be performed on the FAS.

The data will be presented in the below outputs, the TFL number refers to the TFL number in the accompanying TFL shell document:

TFL number	Title
TABLES	
15.2.4.20	Descriptive Statistics of QSU-brief Factors and Total Scores – FAS
15.2.4.21	Analysis of QSU-brief Factors and Total Scores – FAS
FIGURES	
15.1.2.31	QSU-brief Factors and Total Scores Arithmetic Mean and 95% CI – FAS
15.1.2.32	QSU-brief Factors and Total Scores Arithmetic Least Squares Mean Differences and 95% CI – FAS
LISTINGS	
15.3.6.11	Listing of QSU-brief Questionnaire Results and Changes from Baseline

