9 CHANGES FROM THE PROTOCOL SPECIFIED STATISTICAL ANALYSIS

Shift tables for safety endpoints will not be produced for this study. The relevant information provided in the listings is considered to be sufficient. Reason for change: the duration of the study would not allow for seeing trends in shifts tables.

Statistical analysis for the QSU-brief questionnaire data, MNWS questionnaire data and the MCEQ questionnaire data will be performed including interaction terms for product and time point to enable least square means to be calculated at each time point in order to explore the pattern of the CHTP 1.0 effect over time. The main comparison between products will be the comparison over all of the time points. Reason for change: this analysis would capture the daily evolution of perception of the product and the adaptation process taking into account the subjects' repeated measurements.

The second exploratory objective ("To evaluate the relationship between the levels of BoExp in 24-hour urine on Day 5 and NEQ in smokers switching from CC to CHTP 1.0, and in smokers continuing smoking CC") will be reported in a separate report. Reason for change: this analysis would be supportive only of analyses not accounting for NEQ difference between exposure groups.

A sensitivity analysis using the PP Population will be performed for every non-safety objective. This will be done if the FAS is not equal to the PP Population. If this is the case, then the table numbering as presented below will be adapted so that a ".1" is added to the FAS table and a ".2" is added to the PP table. Reason for change: the analysis on PP population would allow interpretability with studies in which PP population would be the primary set for analysis. The protocol was planning this analysis to be carried out only if

the PP population would differ from the FAS by more than 20%. It was decided to present the analyses for both FAS and PP regardless of difference in size between the two populations. .

The term “adjusted to creatinine” has been replaced by “adjusted for creatinine” in all relevant endpoints and analyses. Reason for change: the term was considered more grammatically correct than the original one from the protocol.

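### QSU-brief: the p > 0.1 rule for dropping product-by-time, together with the printed SAS code, withholds the model-based daily CHTP-CC contrasts that the SAP promises

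*SAP*

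**What the plan says.** SAP 9 announces that the QSU-brief, MNWS and MCEQ analyses will contain "interaction terms for product and time point to enable least square means to be calculated at each time point", so that the course of the CHTP 1.0 effect can be explored. It mentions no removal of the term. It also ranks the comparisons: "The main comparison between products will be the comparison over all of the time points".

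SAP 12.5.3.1.1 (QSU-brief) states "The analysis will compare each post baseline timepoint in the domain and total scores". Its text lists product, time point and their interaction as model terms, then adds "The interaction term will be removed if $p > 0.1". The code printed beneath has `product product*time_point` in the MODEL statement, with no `time_point` on its own. Its only LS-means request is "Lsmean product / diff alpha=0.05 cl".

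SAP 12.5.3.1.2 (MCEQ) and 12.5.3.1.3 (MNWS) list the same terms without a removal rule and say that their code is the same as in 12.5.3.1.1. SAP 12.5.2.1.2 has the same rule and the same code structure for the supplementary NEQ model. SAP 12.5.2.2 applies that model to plasma nicotine and cotinine by reference.

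**The concern.** The interaction is in the QSU-brief model for one stated purpose: to obtain arm comparisons at each time point. The removal rule makes that output conditional on a test for which the trial has no planned power. If p exceeds 0.1, one common difference is fitted to Days 1 to 5 and no daily contrast can be formed from the model.

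The code raises two further problems. Without a `time_point` main effect, `product*time_point` absorbs the time course common to both arms, so its p-value does not test the interaction alone, and deleting the term also deletes time from the model. With LS means requested for product only, the daily contrasts are not printed even when the interaction stays.

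At stake is whether the SAP answers its own question about daily evolution and adaptation after the switch. No confirmatory claim depends on it.

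**Working it through.** **1. What the sample size covers.** SAP 8 gives 40 per arm and, for COHb, mean ratio 0.40 and CV 0.32, with a one-sided 2.5% test against a 50% reduction.

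- Log-SD = √ln(1 + 0.32²) = 0.312.
- Distance = ln(0.50/0.40) = 0.223.
- Noncentrality = 0.223 / (0.312 × √(2/40)) = 3.20.
- Power = 88.4% (noncentral t, 78 df) or 89.2% (normal).

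The stated 88% reproduces. It concerns primary biomarkers only; no power is given for any product-by-time test.

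**2. How often a pure interaction test misses a drift.** Take the model as the SAP text describes it, with time in the model: 5 days, 4-df test at 0.10, denominator df 75 (multivariate test, unstructured covariance). The documents give no QSU-brief SD or within-subject correlation ρ, so both are assumed. Let the arm difference fall linearly from 0.5 SD to 0: 0.5, 0.375, 0.25, 0.125, 0. Its sum of squares about the mean is 2 × 0.25² + 2 × 0.125² = 0.15625.

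Under compound symmetry (CS), noncentrality = (40/2) × 0.15625 / (1 − ρ). At ρ = 0.5 this is 6.25. Under AR(1) it is the same quadratic form with V = (2/40)Σ.

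| ρ | 0.3 | 0.5 | 0.6 | 0.7 |
|---|---|---|---|---|
| CS noncentrality | 4.46 | 6.25 | 7.81 | 10.42 |
| CS, term removed | 54% | 41% | 31% | 19% |
| AR(1) noncentrality | 2.67 | 2.71 | 2.89 | 3.30 |
| AR(1), term removed | 68% | 68% | 66% | 63% |

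A change from 0.8 SD to 0 is rarely missed (6% or less for CS with ρ of 0.5 or more). One from 0.3 SD to 0 is missed in 72% of trials at ρ = 0.5 (CS).

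**3. What the printed code tests.** The design matrix for product alone has rank 2; with `product*time_point` added it has rank 10. The tested term therefore has 8 df, not 4, and contains the shared time trend.

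- No interaction, but both arms rise by 0.4 SD over the five days: noncentrality = 2 × 40 × 0.10 / 0.5 = 16 (CS, ρ = 0.5). The term is retained in about 87–89% of trials, depending on the denominator df, although no interaction exists.
- The 0.5-SD drift occurring wholly in one arm, the other flat: noncentrality = 40 × 0.15625 / 0.5 = 12.5. The term is removed in about 20–23% of trials, against 41% for the pure test.

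The decision thus depends on whether the text or the code is followed.

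**4. The comparison over all time points.** Trials were simulated under the step 2 drift and those in which the 4-df test led to removal were kept. The common-difference 95% CI covers the true mean difference over Days 1 to 5 in about 93–94% of them (CS and AR(1), ρ 0.3–0.7). Read as an interval for Day 1 or Day 5, it covers in about 58–68% at ρ = 0.5.

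**5. What the reported average means.** With the interaction kept, LS means for product weight the five days equally. With it removed, the estimate is weighted by the inverse covariance. Under AR(1) with ρ = 0.5 the weights are 2/7, 1/7, 1/7, 1/7, 2/7. For a difference of 0 on Day 1 and 0.5 SD afterwards, the equal-weight average is 0.5 × 4/5 = 0.40 SD and the covariance-weighted one is 0.5 × 5/7 = 0.36 SD.

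**The case against.** The strongest reply is that SAP 9 makes the comparison over all time points the main one, and step 4 shows it is practically unharmed. That stands. The 58–68% figure is no evidence against the main comparison, because the SAP never offers the pooled interval as a Day 1 or Day 5 interval.

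Daily information does not vanish either. Daily arm means for QSU-brief remain in Table 15.2.4.20, and Figure 15.1.2.31 plots means with 95% CIs. This also stands, but raw arm means are not the baseline-adjusted comparisons that SAP 9 and 12.5.3.1.1 promise.

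Four stronger readings are tempting and are not supported:

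- *That the SAP treats non-significance as proof of a constant effect.* It states a prespecified model-reduction rule and claims no equivalence.
- *That promised daily comparisons of NEQ and plasma nicotine/cotinine are lost.* SAP 9 describes those analyses as covering the exposure period as a whole and promises no daily contrast. The Day 5 comparisons have their own models in 12.5.2.1.2 and 12.5.2.2, without the rule. The 16 h half-life in protocol Appendix D makes a constant NEQ difference doubtful, but the target there is an average. The rule only lets the pretest decide how that average is weighted (step 5).
- *That MCEQ and MNWS are deliberately exempt.* Their text omits the rule but reuses the QSU-brief code, so the silence may be abbreviation.
- *That deleting the removal sentence is enough.* The code would still print no daily contrasts.

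**Conclusion.** The point holds, at minor to moderate weight. For QSU-brief, the removal rule conflicts with SAP 9 and with the opening of the same analysis paragraph, and it rests on a test that was never powered. Under the assumed 0.5-SD linear drift, the daily contrasts would be dropped in about 19–54% (CS) or 63–68% (AR(1)) of trials. These rates depend on assumed drift, SD and correlation, and on fitting time as the text says rather than as the code does; large drifts would seldom be missed.

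The code faults are independent of those assumptions. As printed, it neither tests the interaction alone nor outputs daily contrasts, and MCEQ and MNWS inherit both faults. For NEQ and plasma nicotine/cotinine, the consequence of the rule is limited to an average whose weighting depends on the pretest. A reader might infer that the main questionnaire comparison, the Day 5 analyses or the primary endpoints and their alpha are compromised; none of them is.

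**What to change.** 1. In SAP 12.5.2.1.2 and 12.5.3.1.1, delete the sentence that removes the interaction when p > 0.1. Report the interaction p-value as description only.
2. In both MODEL statements, use `product time_point product*time_point`, as the text already describes.
3. Request LS means for `product` (the equal-weight average over Days 1 to 5, named as the main comparison) and for `product*time_point`.
4. For QSU-brief, MCEQ and MNWS, report the CHTP − CC difference with its 95% CI at each post-baseline day.

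The cost is an edit to two code blocks, two deleted sentences and a few more output rows. The overall contrast may be slightly less precise than the covariance-weighted one if the effect really is constant. No new data are needed.

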7 DERIVED AND COMPUTED VARIABLES

Mean change from baseline (baseline is defined in Section 12.1.4 “Definitions for Statistical Data Analysis”) is the mean of all individual subjects’ change from baseline values. Each individual change from baseline will be calculated by subtracting the individual subject’s baseline value from the value at the timepoint.

Mean percent change from baseline is the mean of all individual subjects’ percent change from baseline values. Each percent change from baseline will be calculated by subtracting the individual subject’s baseline value from the value at the desired timepoint and then

dividing this calculated value by the individual subject's baseline value and multiplying by 100.

When the baseline value is 0, 1 will be used in the denominator for calculating the percent change from baseline.

The QT interval corrected using Bazett's formula (QTcB) will be calculated as follows:

$$QTcB = \frac{QT}{\sqrt{\left(\frac{60}{HR}\right)}}$$

The QT interval corrected using Fridericia's formula (QTcF) will be calculated as follows:

$$QTcF = \frac{QT}{\sqrt[3]{\left(\frac{60}{HR}\right)}}$$

Reported BMI will be calculated at site from the body weight and height using the following formula:

$$BMI = \frac{\text{weight in kilograms}}{\text{height in meters}^2} \quad (\text{kg/m}^2)$$

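### The SAS code prescribed for QSU-brief, MCEQ and MNWS does not match the SAP text: undefined response, no time-point main effect, and no daily contrasts requested

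*SAP*

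**What the plan says.** SAP section 9 declares a change from the protocol for the three questionnaires. Product-by-time terms are added "to enable least square means to be calculated at each time point", so that the pattern of the CHTP 1.0 effect over time can be explored. The same section sets the hierarchy: "The main comparison between products will be the comparison over all of the time points".

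SAP 12.5.3.1.1 (QSU-brief) then states "The analysis will compare each post baseline timepoint in the domain and total scores". It lists the model terms as baseline score, sex, cigarette consumption, product, time point and the product-by-time interaction, and says the interaction is dropped if p > 0.1. On output it says "LS means for each product along with the difference (CHTP - CC) with 95% CI will be presented in the tables".

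The code given there for use has the response line "Model reduction = base_QSU sex cigarette_cons product", continued by `product*time_point`. Its LS means request is "Lsmean product / diff alpha=0.05 cl".

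SAP 12.5.3.1.2 (MCEQ) and 12.5.3.1.3 (MNWS) repeat the commitment to compare every post-baseline time point and refer back to this code. Neither states a removal rule for the interaction.

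**The concern.** The text and the code describe different analyses in three respects.

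- **Response.** The text analyses scores; the code analyses `reduction`. Elsewhere the SAP uses that word for a between-arm percentage, "the reduction (i.e: 100% - ratio of CHTP : CC", in 12.5.1, and in the same sense in 12.5.2.1.2 and 12.5.3.2. A between-arm percentage cannot be a per-subject response.
- **Output.** The daily arm differences are the reason section 9 gives for changing the model, but the code does not request them.
- **Model terms.** The text lists time point as a term in its own right; the Model statement does not contain it.

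At stake are the direction in which craving, withdrawal and product-satisfaction differences are printed, and whether the day-by-day pattern is reported. If the code is followed literally, both depend on what the programmer infers.

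**Working it through.** The documents give no power or sample-size figure for these endpoints, so there is no stated number to reproduce. The check compares code with text.

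**1. Sign of the product effect.** Write the score model as y = a + βb + (other terms) + δP, with b the baseline, P = 1 for CHTP 1.0 and P = 0 for CC.

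- Response y: product coefficient δ.
- Response y - b: baseline slope β - 1, product coefficient δ. SAP section 7 defines change this way, by subtracting the subject's "baseline value from the value at the timepoint".
- Response b - y: baseline slope 1 - β, product coefficient -δ.

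Score and change therefore agree, and baseline minus score gives the exact negative. A simulated example (40 per arm, 5 days, effect sizes and SDs assumed, same mean structure fitted by ordinary least squares) gave these CHTP - CC differences:

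| Response | Overall | Day 1 | Day 2 | Day 3 | Day 4 | Day 5 |
|---|---|---|---|---|---|---|
| Score | +0.381 | +0.802 | +0.659 | +0.553 | -0.031 | -0.077 |
| Score minus baseline | +0.381 | +0.802 | +0.659 | +0.553 | -0.031 | -0.077 |
| Baseline minus score | -0.381 | -0.802 | -0.659 | -0.553 | +0.031 | +0.077 |

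The values only illustrate the identity. They also show what an overall mean can hide: (0.802 + 0.659 + 0.553 - 0.031 - 0.077)/5 = 0.381.

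**2. Order of subtraction.** The primary code in SAP 12.5.1.1 names CC as the control level. The questionnaire code uses plain `diff`, which follows the order of the class levels. If the levels sort alphabetically (CC, then CHTP), the printed difference is CC - CHTP, a second possible reversal.

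**3. Estimates requested.** LS means for product give 2 means and 1 difference, averaged over days. LS means for product by time point over Days 1 to 5 give 2 × 5 = 10 means, from which 5 within-day differences follow. The code requests 0 of these 5 for each score. The scores affected are QSU-brief 3 (total and two factors), MCEQ 5 and MNWS 2, or 10 in all; 10 × 5 = 50 daily contrasts.

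**4. Missing time-point term.** With `time_point` in the model, the interaction has (2 - 1)(5 - 1) = 4 degrees of freedom. Without it, `product*time_point` has 2 × (5 - 1) = 8, because it carries time and interaction together. While the term stays in, the fit is unchanged: 1 + 1 + 8 = 10 cell means, the same as 1 + 1 + 4 + 4 = 10. The harm comes with the QSU-brief rule. The test at p > 0.1 is then on the 8-df term, so a time trend common to both arms could keep it with no interaction present. If the term is removed, time leaves the model altogether.

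**The case against.** The strongest reply is that the code is only a sketch and the text governs. It uses a placeholder data set name, and the primary code has a response term that would not run as written. The text still requires the daily comparisons. Figures 15.1.2.32 and 15.1.2.36 list LS mean differences and Figure 15.1.2.34 lists LS means, and table layouts sit in a separate shell document. The direction is fixed in words as CHTP - CC, section 7 defines change as value minus baseline, and raw-mean profiles would expose a flipped sign. The main comparison over all time points is exactly what the code delivers.

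Most of this stands, and it rules out two stronger readings. A reader might infer that the daily analysis is absent from the plan. It is not: section 9 and all three questionnaire sections call for it. A reader might also infer that arm differences will be printed with the wrong sign. The documents do not show that either: reversal needs `reduction` to be built as baseline minus score, or an unfavourable class-level order, and the text points the other way.

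The reply does not remove the mismatch. The SAP presents this as the code to be used, and followed literally it gives neither the named response nor the daily estimates.

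**Conclusion.** The point holds as a conflict between prescribed code and text, at low priority. As written, the code yields the main overall comparison and none of the 5 daily CHTP - CC contrasts for each of 10 scores. Its response is undefined, so the direction of the difference is not secured by the code; a reversal would change the sign and leave the size unchanged. The omitted time-point term makes the QSU-brief removal rule act on an 8-df term instead of the 4-df interaction. For MCEQ and MNWS, which have no removal rule, the omission alters the printed test but not the estimates.

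The count of five days assumes reported Days 1 to 5 for every questionnaire. The endpoints are exploratory, and this questionnaire code feeds no primary or secondary analysis.

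**What to change.** In SAP 12.5.3.1.1, with the references in 12.5.3.1.2 and 12.5.3.1.3 carried through:

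1. Name the response as the post-baseline score, or as score minus baseline.
2. Add `time_point` to the Model statement alongside `product` and `product*time_point`.
3. Keep the overall product contrast as the main comparison, with CC fixed: `diff=control('CC')`.
4. Request LS means for `product*time_point`, with explicit within-day CHTP - CC contrasts through ESTIMATE or LSMESTIMATE statements, or by selecting the within-day pairs from `diff`. Do not use `diff=control` on the interaction: it compares the other 9 cells with one reference cell, and only 1 of those 9 differences is a within-day CHTP - CC contrast.
5. For QSU-brief, report the daily estimates from the model that retains the interaction, since section 9 requires them. The p > 0.1 rule may still apply to the overall comparison.

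The cost is a few lines of code and a short SAP edit, with no new data. The NEQ model in SAP 12.5.2.1.2 is also written without `time_point`; that is a separate matter, but it can be checked in the same edit.
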